## **E. Data Analysis**

tDCS-only: Measures of cognitive and emotional states will be compared within subjects for sham vs. active tDCS. These changes may also be correlated with trait measures.

**tDCS+fMRI:** Our fMRI data will be analyzed with Statistical Parametric Mapping v.8 (SPM8). We will first conduct a hypothesis-driven region of interest (ROI) analysis (Bonferroni-corrected alphas for multiple VOIs) to examine brain areas previously shown to be activated during rejection including the rVLPFC, anterior insula, and dorsal anterior cingulate. We will compare rejection-neutral contrasts between runs and sessions, in a within-subjects analysis. We will also conduct a whole-brain analysis in a voxel-by-voxel brain-wide search. Statistical parametric maps are obtained using whole-brain image subtraction routines with the images warped to MNI standardized space. Differences between tDCS and sham are then mapped into stereotactic space using t-maps of statistical significance using a general linear model. RS as a covariate will also be tested in both the VOI and whole-brain analyses.

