## **D. Research Design and Methods**

### *1. Rationale/Overview*

We will first test the behavioral effects of tDCS during the Social Feedback Task without fMRI in a sample of up to 30 subjects. After establishing the behavioral effects of tDCS-only (Aim 1), we will test a separate group of up to 30 subjects using tDCS plus fMRI (Aim 2).

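### Bonferroni over the VOIs is valid but needlessly conservative: Holm's step-down test keeps the same familywise bound and can detect more regions

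*Combined protocol and SAP*

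**What the plan says.** Section E (Data Analysis), tDCS+fMRI paragraph, begins with a hypothesis-driven region-of-interest analysis using "Bonferroni-corrected alphas for multiple VOIs". The regions are given as areas "including the rVLPFC, anterior insula, and dorsal anterior cingulate", so three are named and the list is left open. The comparison is described thus: "We will compare rejection-neutral contrasts between runs and sessions, in a within-subjects analysis". RS is also to be tested as a covariate in the VOI analysis. Section D.1 sets the sample for this aim: "we will test a separate group of up to 30 subjects using tDCS plus fMRI (Aim 2").

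The documents name no step-down, step-up, false-discovery or gatekeeping procedure. They do not state the familywise alpha, whether tests are two-sided, the final number of VOIs, an expected effect size, or a power calculation.

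**The concern.** Bonferroni holds every VOI to alpha divided by the number of VOIs, however many have already been declared significant. Holm applies that threshold only to the smallest p-value and relaxes it for each later one. Both control the familywise error without any assumption about how the regions are correlated, so the stricter thresholds for the second and later regions buy no better guarantee.

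What is at stake is the power to find the second and third region. Aim 2 is to identify neural pathways, in the plural, so which regions respond is of interest as well as whether any does. The sample is at most 30, with no documented power margin. The specific aims also allow other stimulation sites in separate subjects, which could leave fewer subjects per site.

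**Working it through.** **Inputs from the documents.** Bonferroni over the VOIs; three named VOIs, list open; within-subject comparison of active and sham; up to 30 subjects. There is no stated power or alpha to reproduce.

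**Inputs assumed.** Familywise two-sided alpha 0.05; one paired t-test per VOI on the active-minus-sham difference in the rejection-neutral contrast; standardised effect d = 0.5 (0.3 and 0.7 as a range); between-VOI correlation 0.5 (0 as a check); n = 30, with n = 20 because 30 is a ceiling; m = 3 VOIs, with m = 6 because the list is open.

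**Thresholds for m = 3.**
- Bonferroni: 0.05/3 = 0.0167 for every VOI.
- Holm: ordered p-values against 0.05/3 = 0.0167, 0.05/2 = 0.025, 0.05/1 = 0.05, stopping at the first failure.

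Holm's first threshold is Bonferroni's and the later ones are looser, so no Bonferroni rejection can be lost.

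**Why the bound is kept.** Suppose m0 of the m nulls are true. When Holm first rejects a true null, at most m − m0 hypotheses have been rejected before it, so the threshold then is at most 0.05/m0. A false rejection therefore needs at least one of m0 true-null p-values to be at or below 0.05/m0. The probability of that is at most m0 × 0.05/m0 = 0.05, under any dependence.

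**Bonferroni power per VOI, in closed form.** The paired t statistic is noncentral t with n − 1 degrees of freedom and noncentrality d√n. For n = 30 and d = 0.5 the noncentrality is 0.5 × √30 = 2.74 and the critical value at 0.0167 is 2.54, giving power 58%. For n = 20 it is 0.5 × √20 = 2.24 against 2.63, giving 37%.

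**Bonferroni against Holm, by simulation** (20,000 to 50,000 replicates per setting; Monte Carlo standard error at most about 0.4 points). m = 3, d = 0.5, correlation 0.5:

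| Setting | Average power per affected VOI | Power for all affected VOIs | At least one VOI rejected |
|---|---|---|---|
| n = 30, all three respond | 58% → 67% | 33% → 52% | 82.5% → 82.5% |
| n = 30, two respond | 58% → 62% | 41% → 48% | 75% → 75% |
| n = 30, one responds | 57.8% → 57.9% | same | 59% → 59% |
| n = 20, all three respond | 37% → 44% | 14% → 27% | 63% → 63% |

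**Range, all VOIs responding, correlation 0.5, n = 30.**
- d = 0.3: average 20.5% → 24.3%; all three 4.7% → 11.5%.
- d = 0.7: average 89.3% → 94.3%; all three 76.5% → 89.2%.
- m = 6, d = 0.5: average 47% → 58%; all six 12% → 34%.

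At correlation 0 (m = 3, d = 0.5) the average goes from 58% to 68% and all three from 20% to 40%.

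**Actual familywise error, n = 30.** With no true effects the two methods agree: 0.050 at correlation 0 and 0.044 at correlation 0.5. With d = 0.5, correlation 0.5 and two of three responding, it is 0.018 under Bonferroni and 0.037 under Holm. With one responding, it is 0.033 and 0.042. The largest Holm value in a mixed setting was 0.0475 (d = 0.7 in two VOIs, correlation 0).

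**The case against.** Bonferroni is valid and stated in advance, so there is no error to correct. The largest gains need all three regions to respond equally, and the documents do not make declaring all three a criterion of success. Part of Holm's extra power comes from spending error allowance that Bonferroni leaves unused. Bonferroni also has simple matching simultaneous confidence intervals, which Holm lacks. And Holm needs a closed family of tests, which Section E does not give.

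Much of this stands, and it rules out three stronger readings.

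- A reader might infer that Aim 2 in general gains 9 points of power per region, or 19 points for the full set. Those figures hold only if all three regions respond. With one affected region, and for finding at least one, there is in effect nothing to gain.
- A reader might infer that the error rate is untouched. The nominal bound is the same; the actual rate rises towards it when some regions respond and others do not.
- A reader might take 0.0167 as the plan's own threshold. The documents give neither the familywise alpha nor a closed list of VOIs.

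None of this shows a cost of Holm for this plan. No simultaneous intervals are planned, so none are lost. The open list is a real gap and matters more than the choice of procedure, but Bonferroni needs the same list closed, since its divisor is also the number of tests.

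**Conclusion.** The point holds as a free improvement in efficiency, not as a flaw. That Holm keeps the bound and loses no Bonferroni rejection is certain for any fixed set of VOIs with valid p-values. The size of the gain is conditional. It lies wholly in the second and later regions and depends on how many truly respond: about 9 points of average power if all three do, about 4 if two do, and practically none if one does. These figures rest on the assumed alpha, paired t-test per VOI, effect, correlation and sample size. Section E does not say whether each VOI is averaged to one value or tested voxel by voxel; the calculation takes one value per VOI. With 20 subjects and all three affected the gain is about 7 points on a lower base (37% to 44%).

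**What to change.** In Section E, replace "Bonferroni-corrected alphas for multiple VOIs" with wording to this effect: *Holm-adjusted p-values (familywise two-sided alpha 0.05) for the active-sham difference in the rejection-neutral contrast over the VOIs, whose list is fixed before analysis (rVLPFC, anterior insula, dorsal anterior cingulate, and any others named in advance).* Keep a multiplicity correction, with Holm in place of Bonferroni, for the between-run and RS-covariate VOI tests, so that narrowing the main family does not leave them uncorrected.

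The cost is a sentence or two in Section E and a decision on the VOI list, which Bonferroni would need as well. No subjects, scans or procedures are added, and the nominal familywise bound stays where it was.

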## **F. Funding Status, Details**

To conduct this project, the PI has received a pilot grant from the Department of Psychiatry Pilot Grant Program. The purpose of this pilot grant is to acquire preliminary data for extramural funding for testing additional subjects as well as psychiatric populations.

## **G. Human Subjects Research Protection from Risk**

**tDCS risks and minimization of risk:** tDCS is performed by placing electrodes upon the scalp and applying a small electrical current in order to affect brain function. The maximum amount of current that subjects would receive in our study is 2 milliamps, and each tDCS session can last up to about 30 minutes. As a point of reference, small hearing aids run on approximately 2.4 milliamps. At this level of current and duration of tDCS stimulation, possible side effects are expected to be mild, benign, and short-lived. In a review of 74 studies reporting adverse effects of tDCS, the most common side effects were itching (39%), tingling (22%), headache (15%), burning sensation (9%), and discomfort (10%).

Other studies have shown that tDCS does not elevate serum levels of molecular markers of neuronal injury such as neuron-specific enolase or N-acetyl-aspartate. Both contrast-enhanced MRI and EEG studies have found no pathological changes associated with application of tDCS. In contrast to other forms of transcranial electrical stimulation such as transcranial magnetic stimulation (TMS), tDCS has never been shown to cause epileptic seizures, even in patients with refractory epilepsy. Finally, certain electrode positions, specifically those close to the mastoid process (the raised part of the skull behind the ear), can sometimes influence the vestibular system and cause nausea and/or vertigo. Our staff is well trained in proper administration of tDCS, and the electrode positions to be used in this study will not be near the mastoid process.

**Risk of Interviews, Questionnaires, Social Feedback Task, and Minimization of Risk:** The questions asked concerning mood and mental states are without risk, but may be considered repetitive. Some of the questions may be perceived as embarrassing or make subjects feel uncomfortable. Subjects are also informed that they have access to clinical services if discussion of personal history during the screening interview becomes emotionally intolerable. As with any part of this protocol, subjects may refuse to answer these questions, although doing so may mean that they cannot participate. Research interviews will be interrupted if participants become distressed or object to answering questions. They will be informed that these procedures can be stopped at any time, temporarily or permanently, as necessary.

During the Social Feedback Task, subjects receive feedback on a scale of likability on how others rated their self-completed profile. The ratings given to subjects are not real: they are created and compiled by the experimenter. However, we will ask subjects to imagine that they are real. Some ratings may make subjects feel upset. We expect these feelings to be momentary and do not expect them to carry over after the experiments. However, subjects will be advised to notify the researcher immediately if they continue to feel upset upon completion of the study. If subjects experience any suicidal thoughts or feel that they are in

imminent danger of harming his/herself, they will be advised to contact the Stony Brook University Comprehensive Psychiatric Emergency Program (CPEP) [contact]), a hospital-based emergency psychiatric service open 24 hours a day, 7 days per week.

As with any research study, there may be additional risks that are unknown or unexpected.

**fMRI risks and minimization of risk:** This type of imaging requires the use of magnetic pulses to obtain information about the structure and function of the brain. This technique is used routinely in clinical practice, and does not involve radiation exposure. Subjects will be instructed to provide information as to the possibility of any surgical clips, pacemakers or implants that may be present in the body. Some medication patches may also overheat causing injury, and subjects will be asked to remove them before scanning. Prior to inclusion in the tDCS+fMRI study, the presence of potential MR risks, such as pacemakers, surgical clips or metallic surgical devices will be excluded by medical and surgical history using a standard review form. Other than those described above, there are no known biological risks due to exposure to the magnetic fields such as those that will be used in this project.

MRI imaging is performed within a machine, or scanner, which can feel quite confining. This may cause nervousness or severe claustrophobia in some subjects, which may require withdrawal from the study, or even medical treatment. There is the potential that a magnetic resonance image may reveal an abnormality that is already in the body, such as a cyst or tumor. Many such abnormalities are not clinically significant, but subjects will be informed that they may need or want to investigate them further. Such a finding might require additional studies, and maybe even treatment, neither of which would be paid for by the investigators, the sponsor, or Stony Brook University.

The MRI scanner makes loud, vibrating noises. Subjects will wear foam earplugs to reduce the loud noises made by the scanner and prevent any hearing damage. Some studies, like this one, have the potential to cause “peripheral nerve stimulation” (PNS). PNS is a light touching sensation on the skin surface, lasting only for a few seconds. It may cause mild discomfort, but is not harmful. The MRI machine is operated within FDA guidelines so the potential for inducing PNS is low.

Sometimes, subjects report a temporary, slight dizziness, light-headedness or nausea during or immediately after the scanning session. If a subject feels dizzy or light-headed, he or she will be instructed to get up slowly from the scanner.

**Incidental Findings:** The following language is included in the consent form for the fMRI studies:

The discovery of an incidental finding may cause you to feel anxious. If you have further tests done by your medical doctor, those results will then become part of your medical record, which may affect current and future health or life insurance. The costs for any care that will be needed to diagnose or treat an incidental finding would not be paid for by this research study. These costs would be your responsibility (financial assistance programs are available, should you need help)."

Subjects are asked to mark the checkbox for "yes" or "no", sign, and date, for the question: "Do you agree to be informed of any incidental findings discovered during the course of this research study?"

**Confidentiality of Subject Records:** All study-specific data collected will be kept confidential and used for research purposes only. Each participant will be assigned a coded identifier that will be used to associate stored data with each participant. Questionnaires, forms, and results of medical and laboratory tests will contain the patient's ID number and initials on each page; no other identifying information will be included on the data forms. Diagnostic interviewers will only enter coded identifiers and initials on their notes and forms. The only forms that will contain the participants' names and identifying information are the consent forms, which will be stored in a locked file in a locked office of the research team. The list associating participants' names with coded identifiers will be maintained separately from the data and in a locked or password-protected file. No participant's identifying data will be published.

All electronic records will be kept confidential to the extent permitted by law. This database is password protected and only study personnel will be given the password. All files (including linking files) on laptop computers containing identifiers will be encrypted using software packages supported by Stony Brook University. Only study personnel will have access to the database and backup. Data will be kept up to 7 years. Subject names and diagnoses are stored in electronic databases that are accessible only with a password. Only the research staff involved in the studies at the Stony Brook Medical Center has access to the databases. Subject names, along with scan information are stored on desktop computers and workstations at these locations. These computers are encrypted and kept in locked offices. The MR images of subjects will be reviewed by the research team in conjunction with a radiologist and, if necessary, the results will be shared with subjects or a physician who they may designate. If files need to be transferred between sites, encryption protocols will be used.

**Potential Benefits to Subjects:** Subjects will not receive any personal benefits from being in this study. Research information obtained from this study may benefit the subject or others in the future. The risks associated with this study are very low. Data from this study may advance our understanding of the mechanism of recovering from social rejection and therefore contribute to the development of improved treatments for rejection-related disorders such as major depressive, social anxiety, and borderline personality disorders.

